13 RISK/BENEFIT ANALYSIS

13.1 Anticipated Clinical Benefits

It is anticipated that application of the investigational device to a bleeding site will result in a reduced time to hemostasis compared to conventional methods of hemostasis (pressure, suture, or cautery). Individual subjects may not directly benefit from participation in this investigation. However, conducting this research could contribute to the overall advancement of medical and scientific knowledge and may benefit future patients.

13.2 Risks Associated with Participation in the Clinical Investigation

There are possible risks, complications, and discomforts associated with undergoing a surgical procedure. There are also additional risks specifically associated with the surgical arm (cardiothoracic, abdominal, orthopedic lower extremity). The Investigator will be responsible for discussing these risks, complications and discomforts with subjects along with the risks associated with anesthesia.

Adverse events observed during and after the application of a hemostatic agent other than HEMOBLAST™ in a large pivotal clinical trial of 309 patients at a greater than 1% frequency included:

- Anemia;
- Arrhythmia;
- Atelectasis;
- Confusion;
- Dural tear;
- Edema;
- Fever;
- Fibrillation Atrial;
- Fibrillation Ventricular;
- Heart Failure Right;
- Hemorrhage;
- Hypotension;
- Infection;
- Pleural Effusion
- Pneumonia;
- Rash;
- Respiratory distress;
- Thrombosis Arterial; and
- Urinary Tract Infection.

None of the adverse events that occurred were judged by the surgeon to be “Probably Related” to the use of the hemostatic agent.

Adverse events observed during and after the application of a hemostatic agent other than HEMOBLAST™ in a large pivotal clinical trial of 309 patients at a less than 1% frequency included:

- Abscess;
- Acute kidney failure;
- Back pain;
- Bradycardia;
- Cellulitis;
- Cerebrovascular accident;
- Dehiscence;
- Diarrhea;
- Dyspnea;
- Gastritis;
- Hallucination;
- Heart arrest;
- Heel ulcer;
- Hyperglycemia;
- Kidney tubule necrosis;
- Lung edema;
- Myocardial Infarction;
- Nausea;
- Nausea and vomiting;
- Neuropathy;
- Pain;
- Paraesthesia;
- Pneumothorax;
- Rash;
- Skin ulcer;
- Transfusion reaction;
- Urinary Retention; and
- Ventricular Tachycardia.

None of the adverse events that occurred were judged by the surgeon to be “Probably Related” to the use of the hemostatic agent.

Risks possibly related to the use of hemostats similar to HEMOBLAST™ include:

- Adhesion formation
- Allergy or anaphylaxis
- Blockage of cardiopulmonary bypass system;
- Compromised attachment of orthopedic implants;
- Creutzfeldt-Jakob disease (CJD) agent;
- Increased infection;
- Lack of efficacy
- Nerve compression;
- Thrombosis or thromboembolism
- Transmissible Spongiform Encephalopathies (TSE); and
- Viral disease transmission;

Hypersensitivity or allergic/anaphylactoid reactions may occur with HEMOBLAST™. Symptoms associated with allergic anaphylactic reactions include: flush, urticaria, pruritus, nausea, drop in blood pressure, tachycardia or bradycardia, dyspnea, severe hypotension, and anaphylactic shock.

These reactions may occur in patients receiving HEMOBLAST™ for the first time or may increase with repetitive applications of HEMOBLAST™. In the event of hypersensitivity reactions, discontinue administration of HEMOBLAST™. Mild reactions can be managed with antihistamines. Severe hypotensive reactions require immediate intervention using current principles of shock therapy.

Subjects randomized to receive the control are exposed to risks associated with G+T, as described in the current device labeling.

Participation in this clinical investigation also presents additional risks or inconveniences. These may include, but are not limited to:

- An additional blood draw preoperatively and an additional blood draw at 6-week follow-up for antibody evaluation;
- Urine or serum pregnancy test (females of child bearing age) performed preoperatively;
- Additional intraoperative assessments of bleeding severity at 3, 6, and 10 minutes after hemostat application; and
- Follow-up visit at 6 ± 2 weeks postoperatively.

There may also be other unforeseen risks.

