12.1.3 Safety Outcomes

Endpoints used to characterize the safety profile include the rate of occurrence of all AEs and SAEs, reoperation rate due to bleeding, mean volume of intraoperative transfusions, total operative time, mean duration of hospitalization, intraoperative blood product administration, and post-operative blood product administration.

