12.3.2.2 Methods of Analysis

Summaries of the number and percent of subjects with at least one SAE will be provided. Comparisons of the proportion of subjects experiencing SAEs will be made between treatment arms. Summaries of the number of percent of AEs will be provided for each treatment arm.

Differences in mean overall blood loss, mean volume of intra-operative transfusions, mean total operative time, and mean duration of hospitalization will be estimated using linear regression models with stratified adjustment for surgery type and separated by surgery type. In all cases, the robust variance estimator will be used and a 95% Wald-based interval will be computed. Comparisons of the incidence of re-operation (total and reoperation due to bleeding) and the incidence post-surgery bleeding complications will be made using a general linear model to estimate the difference in the probability of each outcome after stratified adjustment for surgery type. Comparisons of the incidence of re-operation and the incidence post-surgery bleeding complications within each surgery type will be made using a two sample binomial test of proportions.

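### The device-class risks named in Protocol 13.2 have no planned between-arm estimate, so an excess in one of them is diluted in the any-SAE comparison

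*Protocol*

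**What the plan says.** Protocol 13.2 lists eleven risks under "Risks possibly related to the use of hemostats similar to HEMOBLAST™ include". They include "Thrombosis or thromboembolism", "Compromised attachment of orthopedic implants", allergy or anaphylaxis, increased infection, nerve compression and adhesion formation. For the study device itself it adds: "Hypersensitivity or allergic/anaphylactoid reactions may occur with HEMOBLAST™".

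The safety endpoints do not draw on that list. Protocol 12.1.3 states: "Endpoints used to characterize the safety profile include the rate of occurrence of all AEs and SAEs, reoperation rate due to bleeding". The remaining endpoints there are transfusion and blood-product use, operative time and hospital stay.

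Protocol 12.3.2.2 and SAP 10.6.2 plan these analyses of events:

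- Any SAE: "Comparisons of the proportion of subjects experiencing SAEs will be made between treatment arms".
- Reoperation and bleeding, by regression: "Comparisons of the incidence of re-operation (total and reoperation due to bleeding) and the incidence post-surgery bleeding complications will be made using a general linear".
- AEs: "Summaries of the number of percent of AEs will be provided for each treatment arm" in the Protocol, and nearly the same sentence in the SAP. Neither states a reporting level, a grouping, a difference or an interval.
- UADEs or SADEs (SAP only): a proportion with a score-based 95% interval, or an exact upper bound if none occur. No arm contrast is stated.

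The CEC (Protocol 8) adjudicates SAEs for relatedness and expectedness, not by type of risk.

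**The concern.** The stated objective is safety and efficacy compared with G+T, yet the harms the sponsor considers plausible for this class have no planned comparison with G+T. In major open surgery many SAEs can be expected from the operation itself. An excess confined to thrombosis or allergy then moves the any-SAE proportion only slightly.

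The routes that look closer to the device are partial. A SADE is defined through a response to an investigational device, so its counterpart in the control arm is unclear. It also needs a relatedness judgment, and SAP 8.3 describes blinding of subjects only. Non-serious allergy or infection falls outside the SADE rate, the any-SAE comparison and CEC review. AE tables by arm would contain the events, but no grouping is fixed. Section 13.2 itself lists infection, pneumonia, urinary tract infection, abscess and cellulitis as separate entries. Pooling such terms after the results are seen would be open to challenge.

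**Working it through.** **The plan's own figure.** The only power stated is 80.1%, for primary non-inferiority. With boundaries 0.788/2.373 and 2.036, information fraction 0.6, 88% in both arms, margin 10% and 267 vs 133, a two-look normal calculation gives 80.0% when the futility boundary is followed. The figure reproduces and is not in dispute. No power or precision is stated for safety.

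**Inputs.** Allocation of 267 vs 133 is from Protocol 6.4.2. Event rates and the background of other SAEs are not in the documents and are assumptions. The background b is set at 10%, 20% and 30%. Named events are taken as all serious and independent of other SAEs, which favours the any-SAE comparison.

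**Formulas.** Any-SAE proportion in an arm with named-risk rate r = 1 − (1 − b)(1 − r). Power = sum of binomial probabilities over all outcomes with pooled z ≥ 1.96 in the direction of harm, where z = (x/267 − y/133) / √[p(1 − p)(1/267 + 1/133)] and p = (x + y)/400.

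**Example of the dilution.** For 1% (G+T) vs 5% (HEMOBLAST) and b = 20%, the any-SAE rates are 1 − 0.80 × 0.99 = 20.8% and 1 − 0.80 × 0.95 = 24.0%. A fivefold ratio becomes 24.0/20.8 = 1.15, and the 4-point difference becomes 3.2 points against a much larger variance.

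| Named risk, G+T vs HEMOBLAST | Direct | Any SAE, b = 10% | b = 20% | b = 30% |
|---|---|---|---|---|
| 1% vs 5% | 56.5% | 15.7% | 10.3% | 8.0% |
| 5% vs 9% | 27.9% | 13.7% | 9.8% | 7.8% |
| 10% vs 14% | 19.2% | 12.5% | 9.4% | 7.7% |
| 1% vs 3% | 18.5% | 6.7% | 5.3% | 4.6% |

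The direct comparison does better in every row. Its advantage narrows as the control rate rises, and a rare single component stays poorly powered.

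**Precision.** Newcombe score-based intervals for illustrative counts:

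- Named event, 11/267 vs 1/133: 3.4 points (95% interval −0.5 to 6.5), width 7.0.
- Any SAE at about 20%, 61/267 vs 27/133: 2.5 points (−6.4 to 10.6), width 17.0. A 3.4-point excess diluted by a 20% background would be 3.4 × 0.80 = 2.7 points, so this is nearly the same harm.
- No events: the exact upper bound 1 − 0.025^(1/n) is 1.4% for n = 267 and 2.7% for n = 133.

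**The case against.** The strongest reply is that the plan already has a device-specific safety analysis. Relatedness is recorded for every AE, the CEC adjudicates every SAE, its adjudications enter the final report (Protocol 11), and the SAP gives the UADE/SADE rate an interval. AEs are also shown for each arm, the IDMC reviews risk and benefit, and SAP 10.8 permits further exploratory analyses. This stands to the extent that serious device-related harm has a partial route to view. It does not supply a randomised contrast, and it does not cover non-serious events.

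A reader might infer that a several-fold excess in a named risk would go unseen, or would probably be reported as no difference in SAEs. The documents do not support that, because such an excess could show in the side-by-side AE summaries or in the UADE/SADE rate.

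A reader might also take the 1% vs 5% row as typical. Section 13.2 lists infection and arterial thrombosis each above 1% in a 309-patient trial of another hemostat, so a composite control rate of 1% is implausible and the higher rows are more relevant to it. A composite dominated by infection would also mask allergy or nerve compression, which repeats the dilution problem. This objection stands, and it is why the fix leads with the separate risks.

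Finally, power is an awkward argument for a table that tests nothing. That is fair. The powers here measure dilution, and the interval widths are the more direct measure of what the table would add.

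**Conclusion.** The gap is real and modest in consequence. Between-arm event comparisons are planned only for any SAE, reoperation and post-surgery bleeding complications. The named risks are collected and partly visible elsewhere, but without a between-arm estimate. For a 4-point excess, direct power is 56.5% to 19.2% as the control rate goes from 1% to 10%, against 15.7% to 7.7% through any SAE over a 10% to 30% background. These sizes rest on assumed rates, on all named events being serious, and on independence from other SAEs. If some events are not serious, the any-SAE comparison does worse. For rare components (1% vs 3%: 18.5%) neither route is an adequate test, so the case is for pre-specified estimation. The primary efficacy conclusion is not affected.

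**What to change.** In Protocol 12.3.2.2 and SAP 10.6.2:

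- Name the 13.2 risks observable within 6 weeks as events of special interest: thrombosis/thromboembolism, allergy/anaphylaxis, infection, adhesion, nerve compression and compromised implant attachment. Transmissible-agent risks are not realistically assessable in that time.
- Fix the term groupings before unblinding, that is, before any results by arm are seen, and state the coding scheme they rely on, since neither document describes one.
- For randomised treated subjects, report for each risk the counts, the between-arm risk difference and a score-based 95% interval. Show the lead-in subjects (up to 50, all HEMOBLAST) separately.
- Give a composite as supplementary only, with and without infection.
- Label the table exploratory and outside the fixed test sequence.

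The cost is one grouping list and one table, with no added subjects and no alpha. The downsides are a few more unadjusted intervals to interpret, and weak ascertainment of adhesion, nerve compression and implant attachment. The follow-up visit in Protocol 6.6 has no assessment directed at these three, so they depend on spontaneous AE or reoperation reports. The table should say so.

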13.3 Risk/Benefit Analysis

Individual patients may experience no direct benefit from participation in the study. However, potential benefits of HEMOBLAST to be investigated in the study include shorter preparation time, in addition to the other endpoints that will be tested for potential superiority as discussed above. Risk mitigation steps have been taken through investigational device specifications and the performance of non-clinical testing and a clinical study. Risk mitigation steps are also implemented in the manufacture and shipment of the investigational device.

The Sponsor, Medical Expert, and co-ordinating Investigator have determined that this clinical investigation is justified because the potential benefits outweigh the potential risks. Additionally, an IDMC is being put in place to perform continual reviews on the study, including making recommendations based on risk/benefit.

13.4 Conduct of Clinical Investigation to Reduce Risk

Further efforts to minimize risk in this clinical investigation will involve selecting investigators who are experienced and skilled in their respective areas of surgery, have clinical investigation experience, and who are adequately trained on the use of the investigational device and study procedures.

Risks and benefits of this clinical investigation are included in the sample Subject Informed Consent Form, included as Appendix B. Potential risks and benefits will be discussed with potential subjects during the informed consent process.

14 REPORTS AND PUBLICATIONS

14.1 Interim Reports

Interim reports will not be issued during the conduct of this clinical investigation. Thus, if the interim analysis support early termination of the clinical investigation, the number of subjects included may be higher than the number available at the time of the interim analysis. All available data for the analysis populations defined above will be included in the final analysis and report.

14.2 Final Report

The final report will be compiled by the Sponsor or designated Sponsor representative and reviewed, approved and signed off by the co-ordinating investigator.

14.3 Publications

The conduct and results of this clinical investigation will be documented in the final report, as mentioned above. Because this investigation is a multicenter investigation, it is intended that the combined clinical data from all participating sites will be presented and/or published. Individual investigators will not publish or present results prior to publication of the combined multicenter results without prior written consent from the Sponsor. All publications must include the name of the Sponsor (Biom'Up, France).

Detailed publication policies will be included within the Investigator Agreement.

15 ETHICAL CONSIDERATIONS

15.1 Institutional Review Board Approval

Prior to the initiation of this clinical investigation, the Principal Investigator must submit the Clinical Investigational Plan, patient consent form and any other documents as may be required to the appropriate IRB for review and approval. The Principal Investigator, and any other member of the investigational team, must not participate in the decision-making. A signed and dated letter granting IRB approval must be provided to the Sponsor prior to the initiation of the clinical investigation. A list of the members of the IRB reviewing this Clinical Investigational Plan will be requested.

15.2 Informed Consent and Patient Information

The Principal Investigator or designee must explain to each subject the nature of the clinical investigation, including any risks and benefits, its purpose and procedures, and expected duration of involvement in the clinical investigation. Each subject must be informed that participation in the clinical investigation is voluntary and non-participation will not affect his/her right to the most appropriate surgical treatment or affect the doctor/clinician-patient relationship. Subjects have the full right to withdraw from the clinical investigation at any time, irrespective of their initial consent.

Each subject must also give their permission for representatives of the Sponsor, auditor and regulatory authorities to review their hospital records for purposes of source data verification.

15.3 Subject Confidentiality

Confidentiality of subject data will be maintained at all times. Subject anonymity will be guaranteed and all documentation relating to a subject will be kept in a secure location.

15.4 Declaration of Helsinki and IDE Regulations

Outside the United States, this clinical investigation will be conducted in accordance with the relevant articles of the Declaration of Helsinki as adopted by the 18th World Medical Assembly in 1064 and as revised in Tokyo (1975), Venice (1983), Hong Kong (1989), South Africa (1996), Edinburgh (2000), Washington (2002), Tokyo (2004) and Seoul (2008). In the United States, the investigation will be conducted in accordance with applicable FDA regulations and guidance, including 21 CFR Parts 50, 56, and 812.

15.5 Indemnity

The Sponsor recognizes its liability in law to compensate for any injury sustained by a subject participating in this clinical investigation in accordance with applicable laws and guidelines and as agreed upon in the Clinical Trial Agreement which each investigational site.

15.6 Insurance

The Sponsor is responsible for obtaining and maintaining clinical investigation insurance.

16 COMPLIANCE

16.1 Overview

This clinical investigation will be conducted in accordance with Note for Guidance of Good Clinical Practice: CPMP/ICH/135/95.

The following Federal Regulations will also be followed: 21 CFR Parts 11, 50, 56, and 812 and 45 CFR Part 46.

16.2 Clinical Investigation Personnel Responsibilities

Prior to the initiation of this clinical investigation, each Principal Investigator will approve this Clinical Investigational Plan by signing the signature page. This signature confirms that the clinical investigation will be performed in compliance with the Clinical Investigational Plan.

Investigator reporting responsibilities and timelines are included in

Table 11 below. Applicable IRB procedures and any conditions set forth in the Investigator Agreement must also be followed.

Table 11. Investigator Reporting Responsibilities

Responsibility	Report To	Timeline	Details
SAEs, SADEs	Sponsor / Sponsor Representative	24 hours	The Investigator must notify the Sponsor of any SAEs, including those that are potentially device-related, within 24 hours of awareness.
Unanticipated [Serious] Adverse Device Effects (UADEs/USADEs)	Local IRB/EC	10 business days or less and as required by local IRB/EC policy	The Investigator must submit evaluation of any UADE within 10 business days after Investigator awareness and as required by local IRB/EC policy.
	Sponsor / Sponsor Representative	24 hours	The Investigator must notify the Sponsor of any UADE within 24 hours after Investigator awareness.
Withdrawal of IRB/EC approval	Sponsor / Sponsor Representative	5 business days	The Investigator must report a withdrawal of the reviewing IRB approval within 5 business days.
Progress Report	Sponsor and Local IRB/EC	Yearly	Progress reports on the investigation will be submitted to the Sponsor, monitor, and reviewing IRB/EC at regular intervals, but in no event less often than yearly, or as required by local IRB/EC policy.
Deviation from clinical investigational plan in emergency	Sponsor / Sponsor Representative	24 hours	Deviations from the clinical investigational plan that are made to protect the life or physical well-being of a patient in an emergency situation must be reported within 24 hours after the emergency occurred.
	Local IRB/EC	5 business days or less as required by applicable IRB/EC policy	Deviations from the clinical investigational plan that are made to protect the life or physical well-being of a patient in an emergency situation must be reported within 5 business days after the emergency occurred.
Deviation from protocol that affects the scientific soundness of the study plan or the rights, safety, or welfare of human subjects	Sponsor / Sponsor Representative	Prior approval	Prior approval by the Sponsor is required when a deviation of this nature is anticipated.
Failure to obtain informed consent	Sponsor / Sponsor Representative	5 business days	If the investigational device was used without obtaining informed consent, the Investigator must notify the Sponsor within 5 business days of the use of the device.
	Local IRB	5 business days	If the investigational device was used without obtaining informed consent, the Investigator must notify the IRB within 5 business days of the use of the device.
Final report	Sponsor and Local IRB/EC	3 months	The investigators will submit a final report to the Sponsor and local IRB/EC within 3 months after termination or completion of the investigation, or as required by local IRB/EC policy.

The Sponsor shall also provide accurate, complete, and current information about any aspect of the clinical investigation as requested by FDA or reviewing IRB(s).

The Investigator is also responsible for the retention of the clinical investigation records per 21 CFR Parts 812.2(b) and 812.140.

The Sponsor reporting responsibilities and timelines are included in

Table 12 below.

Table 12. Sponsor Reporting Responsibilities

Responsibility	Report To	Timeline	Details
Unanticipated [Serious] Adverse Device Effects (UADEs/USADEs)	FDA, all reviewing IRBs, and Investigators	10 business days	The Sponsor must report the results of an evaluation of a UADE to FDA and all reviewing IRBs and Investigators within 10 business days after Sponsor notification.
Withdrawal of IRB/EC approval	FDA, all reviewing IRBs, and Investigators	5 business days	The Sponsor must notify FDA and all reviewing IRBs and participating Investigators of the withdrawal of IRB/EC approval of an investigation (or any part of an investigation) within 5 business days of receipt of the withdrawal of approval, or as required by applicable national regulations.
Current investigator list	FDA	6 month intervals	The Sponsor will be a current list of the names and addresses of all investigators participating in the investigation 6 months after FDA approval, and at 6 month intervals.
Progress report	Reviewing IRBs	Annually	At regular intervals and at least yearly, the Sponsor must provide progress reports to all reviewing IRBs.
Recall and device disposition	FDA and all reviewing IRBs	30 business days	The Sponsor must notify FDA and all reviewing IRBs of any request that an Investigator return, repair, or dispose of any investigational device. The notice must be made within 30 business days after the request is made and must state why the request was made.
Final report	Reviewing IRBs, and FDA	6 months / 12 months	The Sponsor will submit a final report to FDA and all reviewing IRBs within 6 months after clinical investigation completion or termination.
Informed consent	FDA	5 business days	The Sponsor shall submit to FDA a copy of any report by an investigator of use of a device without obtaining informed consent within 5 business days of receipt of notice of such use.
Significant risk device determination	FDA	5 business days	If an IRB determines that the device is a significant risk device and not a non-significant risk device as the Sponsor had propose to the IRB, a report must be submitted to FDA within 5 business days after the Sponsor learns of the IRB determination.

The Sponsor shall also provide accurate, complete, and current information about any aspect of the clinical investigation as requested by FDA or reviewing IRB(s). Current applicable national regulations shall be followed.

The Sponsor is also responsible for the retention of clinical investigation documentation per 21 CFR Parts 812.2(b) and 812.140 and as required by applicable national regulations.

